16.9 Inclusion of Women and Minorities

16.91 This study will be available to all eligible patients, regardless of race, or ethnic origin.

16.92 There is no information currently available regarding differential effects of this regimen in subsets defined by race, or ethnicity, and there is no reason to expect such differences to exist. Although the planned analysis will, as always, look for differences in treatment effect based on racial groupings, the sample size is not increased in order to provide additional power for subset analyses.

16.93 The geographical region served by the Mayo Clinic, has a population which includes approximately 5% minorities. We expect about 5% of patients will be classified as minorities by race and about 100% of patients will be women.

Accrual Estimates by Gender/Ethnicity/Race

Ethnic Category	Accrual Targets		
	Females	Males	Total
Hispanic or Latino	3	0	3
Not Hispanic or Latino	105	0	105
Hispanic or Latino	5	0	5
Ethnic Category: Total of all subjects	110	0	110
American Indian or Alaskan Native	1	0	1
Asian	1	0	1
Black or African American	1	0	1
Native Hawaiian or other Pacific Islander	0	0	0

Accrual Targets			
Ethnic Category	Sex/Gender		
	Females	Males	Total
White (Hispanic and non-Hispanic)	107	0	107
Racial Category: Total of all subjects	110	0	110

Ethnic Categories: **Hispanic or Latino** – a person of Cuban, Mexican, Puerto Rican, South or Central American, or other Spanish culture or origin, regardless of race. The term “Spanish origin” can also be used in addition to “Hispanic or Latino.”

Not Hispanic or Latino

Racial Categories: **American Indian or Alaskan Native** – a person having origins in any of the original peoples of North, Central, or South America, and who maintains tribal affiliations or community attachment.

Asian – a person having origins in any of the original peoples of the Far East, Southeast Asia, or the Indian subcontinent including, for example, Cambodia, China, India, Japan, Korea, Malaysia, Pakistan, the Philippine Islands, Thailand, and Vietnam. (Note: Individuals from the Philippine Islands have been recorded as Pacific Islanders in previous data collection strategies.)

Black or African American – a person having origins in any of the black racial groups of Africa. Terms such as “Haitian” or “Negro” can be used in addition to “Black or African American.”

Native Hawaiian or other Pacific Islander – a person having origins in any of the original peoples of Hawaii, Guam, Samoa, or other Pacific Islands.

White – a person having origins in any of the original peoples of Europe, the Middle East, or North Africa.

17.0 Pathology Considerations/Tissue Biospecimens

17.1 Summary Table of Research Tissue Specimens to be Collected for this Protocol

None

18.0 Records and Data Collection Procedures

18.1 Submission Timetable

Initial Material(s) -

CRF	Treatment (Compliance with Test Schedule Section 4.0)
Institutional Contacts	
Patient Eligibility	
Demographics	
On-Study	≤2 weeks after registration
On Study: Neoadjuvant Chemotherapy	
Surgery	
Pathology of Ipsilateral Breast	
Adjuvant Therapy	
Adverse Events- Baseline	
Patient Status: Baseline	
Patient Assessment	*6 months after accrual
Off Treatment	Submit ≤2 weeks after registration if withdrawal/refusal occurs prior to beginning protocol therapy

Test Schedule Material(s)

CRF	End of Treatment	12 weeks post/Observation Phase ⁴	Event Monitoring ⁵
Radiation Therapy	X		
Radiation Lumpectomy Therapy	X		
Patient Assessment	X	X	
Adverse Events Solicited	X	X	
Adverse Events: Other	X ²	X ²	
Off Treatment	X ²	X ²	
Patient Status Form	X	X	X

CRF			
	End of Treatment	12 weeks post/Observation Phase ⁴	Event Monitoring ⁵
Specimen Submission: Pathology Report (Recurrence)		X ²	
Consent Withdrawal	X ²	X ²	
Lost to Follow-up	X ²	X ²	
Breast Radiotherapy Questionnaire ³	X	X	

1. Complete at each evaluation during Active Treatment (see Section 4.0).
2. When applicable
3. Survey will need to be entered manually if has not alternately been scanned or entered electronically
4. **Refer to test schedule in section 4.0** If patient has a recurrence prior to being off radiation therapy for 5 years, continue to follow yearly.

18.3 Data Handling and Record Keeping

18.31 Confidentiality

Information about study subjects will be kept confidential and managed according to the requirements of the Health Insurance Portability and Accountability Act of 1996 (HIPAA). Those regulations require a signed subject authorization informing the subject of the following:

- What protected health information (PHI) will be collected from subjects in this study
- Who will have access to that information and why
- Who will use or disclose that information
- The rights of a research subject to revoke their authorization for use of their PHI.

(This information is contained within the Mayo IRB Informed Consent Template Section 14)

In the event that a subject revokes authorization to collect or use PHI, the investigator, by regulation, retains the ability to use all information collected prior to the revocation of subject authorization. For subjects that have revoked authorization to collect or use PHI, attempts should be made to obtain permission to collect at least vital status (long term survival status that the subject is alive) at the end of their scheduled study period.

18.32 Source Documents

Source data is all information, original records of clinical findings, observations, or other activities in a clinical trial necessary for the reconstruction and evaluation of the trial. Source data are contained in source documents.

Examples of these original documents, and data records include: hospital records, clinical and office charts, laboratory notes, memoranda, subjects' diaries or evaluation checklists, pharmacy dispensing records, recorded data from automated instruments, copies or transcriptions certified after verification as

being accurate and complete, microfiches, photographic negatives, microfilm or magnetic media, x-rays, subject files, and records kept at the pharmacy, at the laboratories, and at medico-technical departments involved in the clinical trial. Source documents are kept in a secure location that is locked and requires approved access.

18.33 Case Report Forms

The study case report form (CRF) is the primary data collection instrument for the study. All data requested on the CRF must be recorded. All missing data must be explained. If a space on the CRF is left blank because the procedure was not done or the question was not asked, write "N/D". If the item is not applicable to the individual case, write "N/A". All entries should be printed legibly in black ink. If any entry error has been made, to correct such an error, draw a single straight line through the incorrect entry and enter the correct data above it. All such changes must be initialed and dated. Do not erase or use "white-out" for errors. For clarification of illegible or uncertain entries, print the clarification above the item, then initial and date it. If the reason for the correction is not clear or needs additional explanation, neatly include the details to justify the correction.

18.37 Records Retention

The investigator will maintain records and essential documents related to the conduct of the study. These will include subject case histories and regulatory documents.

The investigator will retain the specified records and reports for;

1. As outlined in the Mayo Clinic Research Policy Manual –"Retention of and Access to Research Data Policy" [REDACTED]

19.0 Study Finances

19.1 Costs charged to patient: routine clinical care

19.2 Other budget concerns: The Mayo Clinic Radiation Oncology Unit is funding the study and will cover costs related to running the study

20.0 Publication Plan

The principal investigators hold primary responsibility for publication of the results of this study and approval from the principal investigators must be obtained before any information can be used or passed on to a third party.

Appendix I
ECOG PERFORMANCE STATUS

Grade

0	Fully active, able to carry on all pre-disease activities without restriction (Karnofsky 90-100).
1	Restricted in physically strenuous activity but ambulatory and able to carry out work of a light or sedentary nature, e.g., light housework, office work (Karnofsky 70-80).
2	Ambulatory and capable of all self-care, but unable to carry out any work activities. Up and about more than 50 percent of waking hours (Karnofsky 50-60).
3	Capable of only limited self-care, confined to bed or chair 50 percent or more of waking hours (Karnofsky 30-40).
4	Completely disabled. Cannot carry on any self-care. Totally confined to bed or chair (Karnofsky 10-20).
5	Dead

Appendix II
Mayo Breast Patient Survey

Mayo Breast Patient Survey

Survey Date (mm/dd/yyyy):

DIRECTIONS: For each question below, please mark one response that describes how you would rate your symptoms DURING THE PAST DAY.

1. How you would describe...

Your overall quality of life? *Response scale 1 to 10, with 1 = as bad as it could be; 10 = as good as it could be*

The severity of your pain, on average? *Response scale 1 to 10, with 1 = no pain; 10 = Pain as bad as it could be*

Your level of fatigue, on average? *Response scale 1 to 10, with 1 = no fatigue; 10 = fatigue as bad as it could be*

DIRECTIONS: For each question below, please mark one response that describes how you would rate your symptoms IN THE LAST 7 DAYS.

2. **In the last 7 days**, how much did anxiety interfere with your usual or daily activities?

- Not at all
- A little bit
- Somewhat
- Quite a bit
- Very much

3. **In the last 7 days**, how much did insomnia, including falling asleep, staying asleep, or waking up early INTERFERE with your usual or daily activities?

- Not at all
- A little bit
- Somewhat
- Quite a bit
- Very much

4. **In the last 7 days**, what was the SEVERITY of your shortness of breath at its WORST?

- Not at all
- A little bit
- Somewhat
- Quite a bit
- Very much

5. **In the last 7 days**, what was the SEVERITY of your cough at its WORST?

- Not at all
- A little bit
- Somewhat
- Quite a bit
- Very much

6. **In the last 7 days**, how much did problems with concentration INTERFERE with your usual or daily activities?

Not at all
A little bit
Somewhat
Quite a bit
Very much

7. **In the last 7 days**, how much did sad or unhappy feelings INTERFERE with your usual or daily activities?

Not at all
A little bit
Somewhat
Quite a bit
Very much

8. **In the last 7 days**, what was the SEVERITY of your skin burns from radiation at their worst?

Not at all
A little bit
Somewhat
Quite a bit
Very much

9. **In the last 7 days**, what was the SEVERITY of your difficulty swallowing at its WORST?

Not at all
A little bit
Somewhat
Quite a bit
Very much

10. **In the last 7 days**, how SEVERE have the following problems been (at their WORST)?

Flaking or peeling of the treated breast or chest wall; *response options 0 to 10, 0 = not at all, 10 = flaking as much as could be*

Bleeding of or leaking fluid from the treatment breast or chest wall; *response options 0 to 10, 0 = not at all, 10 = bleeding as much as could be*

Blistering of the treated breast or chest wall; *response options 0 to 10, 0 = not at all, 10 = blistering as much as could be*

Itching of the treated breast or chest wall; *response options 0 to 10, 0 = not at all, 10 = as itchy as it could be*

Skin burns from radiation on your back; *response options 0 to 10, 0 = not at all, 10 = as itchy as it could be*

11. If you had to do it all over again, would you have this **RADIATION** treatment again?

Yes
No

12. Have you been diagnosed with an infection at your breast cancer surgical site that required treatment with antibiotics or surgery?

Yes
 No

We are interested in your evaluation of your physical appearance and functioning. Please rate the following items from 0 to 10, according to how you feel **AT THIS POINT IN TIME**.

Is the color of your treated breast/chest wall skin different than the other side (red, tan, or lighter)? *response options 0 to 10, 0 = not at all, 10 = as different as it could be*

Do you have visible small blood vessels (spider veins) on your treated breast/chest wall? *response options 0 to 10, 0 = not at all, 10 = as many as it could be*

Do you have pain with swallowing? *response options 0 to 10, 0 = not at all, 10 = as painful as could be*

Do you have numbness or a tingling sensation in the arm on the side that was treated? *response options 0 to 10, 0 = not at all, 10 = as much as it could be*

Do you have tightness, pulling, or stretching in the arm, breast, or chest area (in the side that was treated?) *response options 0 to 10, 0 = not at all, 10 = as much as it could be*

Do you have tenderness or discomfort on the treated breast/chest wall? *response options 0 to 10, 0 = not at all, 10 = as much as it could be*

Overall, how would you rate the cosmetic results of your breast treatment?

Excellent Good Fair Poor

Please rate the following items according to your evaluation **at this point in time**:

Breast/chest wall texture (hardening)	 None	 Slight	 Moderate	 Large
Arm heaviness	 None	 Slight	 Moderate	 Large
Shoulder movement	 None	 Slight	 Moderate	 Large
Arm movement	 None	 Slight	 Moderate	 Large
Breast/chest wall pain	 None	 Slight	 Moderate	 Large
Ability to lift objects	 None	 Slight	 Moderate	 Large
Fit of shirt sleeve	 None	 Slight	 Moderate	 Large
Breast/chest wall tenderness	 None	 Slight	 Moderate	 Large
Shoulder stiffness	 None	 Slight	 Moderate	 Large
Scar tissue	 None	 Slight	 Moderate	 Large
Shoulder pain	 None	 Slight	 Moderate	 Large
Arm pain	 None	 Slight	 Moderate	 Large
Arm swelling	 None	 Slight	 Moderate	 Large
Breast/chest wall swelling	 None	 Slight	 Moderate	 Large
Arm stiffness	 None	 Slight	 Moderate	 Large
Breast/chest wall sensitivity	 None	 Slight	 Moderate	 Large
Fit of clothing	 None	 Slight	 Moderate	 Large
Axillary (arm pit) fullness or numbness	 None	 Slight	 Moderate	 Large

Please complete the following questions if you had breast conserving therapy or mastectomy with reconstruction.

Please rate the following items according to your evaluation **at this point in time**

Breast size	 None	 Slight	 Moderate	 Large
Nipple appearance	 None	 Slight	 Moderate	 Large
Breast shape	 None	 Slight	 Moderate	 Large
Breast elevation (how high the breast is)	 None	 Slight	 Moderate	 Large
Fit of bra	 None	 Slight	 Moderate	 Large
Breast heaviness	 None	 Slight	 Moderate	 Large

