points along with 95% CIs. Comparison between arms will employ a log-rank test.

16.627 *Overall survival:* The OS will be estimated with a Kaplan-Meier estimator and curve by treatment arm. Estimates will be given for specific time points along with 95% CIs. Comparison between arms will employ a log-rank test.

16.631 *Quality of life:* The subscales of the BCTOS, elements from CTCAE-PRO, and other patient reported measures such as fatigue, breast pain, breast shape, and arm related morbidity outlined in the appendix will be summarized as the mean \pm SD and median (minimum value, maximum value). Mixed models will be used to estimate changes at fixed time points as well as compare outcomes between arms.

16.632 *Cosmesis:* The values of the cosmesis instruments (patient self-reported and panel-assessed) will be summarized with the frequencies and confidence intervals of fair or poor cosmesis events at baseline, 2 years, and 5 years by treatment arm. Comparisons between arms will employ chi-squared tests.

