 0	 1	 2	 3	 4	 5	 6	 7	 8	 9	 10
No pain										Worst pain imaginable

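### In Appendix II one burn item carries the itch item's upper anchor, and 10 of the 24 None-to-Large items have no clear scoring direction as printed; exploratory endpoints only.

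*Combined protocol and SAP*

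**What the plan says.** **Burn item.** In Appendix II, question 10, the item on burns of the back reads "Skin burns from radiation on your back; *response options 0 to 10, 0 = not at all, 10 = as itchy". The item directly above it reads "Itching of the treated breast or chest wall; *response options 0 to 10, 0 = not at all, 10 = as itchy as it could be". Question 8 of the same form asks separately "what was the SEVERITY of your skin burns from radiation at their worst", on a five-level verbal scale that does not mention itch.

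**None-to-Large items.** Later in Appendix II, two blocks of items are rated None, Slight, Moderate or Large. Both open with "Please rate the following items according to your evaluation", followed only by a reference to the present moment. The items range from arm pain and arm swelling to "Ability to lift objects", breast size and fit of bra.

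**Use.** Sections 11.3.3 and 11.4.1 say that the questionnaires are adapted from the BCTOS. The adaptation is not described. Section 16.3 uses the BCTOS for functional status (pain, mobility) and for self-reported cosmesis at baseline, 2 and 5 years, all as exploratory endpoints. Section 16.631 covers the BCTOS subscales, PRO-CTCAE elements and "other patient reported measures such as fatigue, breast pain, breast shape, and arm related morbidity outlined in the appendix". It plans means, medians and mixed models for change over time and for comparison of the arms.

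**The concern.** A score can be averaged and compared only if a higher number means the same thing to everyone who answers.

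A patient with a severe burn that does not itch has no correct top category on the burn item.

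On the None-to-Large items, None is plainly the best answer for arm pain. For lifting ability it could mean no ability or no problem. For breast size it means nothing without a reference. If patients resolve this differently, some answers run backwards. A subscale that mixes such items with pain or swelling items then carries extra error, both between patients and within a patient across visits.

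Arm-related morbidity and breast shape, both named in 16.631, draw on these items.

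**Working it through.** The plan gives no figure on this point, so there is nothing to reproduce. The check compares item wording with response anchors and then illustrates the consequence.

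**1. Burn item.** Within question 10, the flaking, bleeding, blistering and itching items each have an upper anchor suited to the symptom. Only the burn item does not; its anchor is that of the itch item above. This is running text, so a broken table cannot explain it. Question 8 covers burn severity in general but does not ask about the back.

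**2. Count of None-to-Large items.** The first block has 18 items (3 from breast texture to shoulder movement, then 15 from arm movement to axillary fullness). The second block has 6. Total: 18 + 6 = 24.

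- Items with no inherent direction in the first block: shoulder movement, arm movement, lifting ability, fit of shirt sleeve, fit of clothing (5).
- In the second block: breast size, nipple appearance, breast shape, breast elevation, fit of bra (5 of the 6).
- Sum: 5 + 5 = 10 of 24, or 42%.

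The stem is also running text and appears twice, both times without reference or direction. The same form shows that a reference can be stated: the skin-colour item asks about difference from the other side.

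**3. Effect on an arm comparison (illustration; all inputs except n are assumptions).** Score None to Large as 1 to 4.

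- Assumed control distribution: 60/25/10/5%, mean 0.60 + 0.50 + 0.30 + 0.20 = 1.60.
- Assumed experimental distribution: 40/30/20/10%, mean 0.40 + 0.60 + 0.60 + 0.40 = 2.00.
- n = 50 per arm (section 16.4), two-sided 0.05.

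If a share m of patients in both arms reads the scale in reverse, each of their scores becomes 5 − x. The observed difference is then (1 − 2m) × 0.40. Power is approximately Φ(difference / (SD × √(2/50)) − 1.96), with √(2/50) = 0.20.

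| m | Difference | SD | Power |
|---|---|---|---|
| 0 | 0.40 | 0.933 | 57% |
| 10% | 0.32 | 1.030 | 34% |
| 20% | 0.24 | 1.100 | 19% |
| 30% | 0.16 | 1.147 | 10% |
| 50% | 0 | 1.183 | no signal left |

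If the arms truly do not differ, (1 − 2m) × 0 = 0 for every m. Ambiguity shared equally by the arms weakens a real contrast and creates no false one.

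**4. Primary endpoint.** It uses grade 3 or higher late adverse events and nurse-scored cosmesis (section 16.21). None of these items enters it or the sample size.

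**The case against.** **Little may turn on the burn item.** The lead-in to question 10 already asks how severe each problem was, question 8 asks about burn severity without the itch anchor, and burns on the back are not named in 2.31, 16.31 or 16.631. This stands as a limit on consequence. It does not make the anchor right. The item is also a standalone 0 to 10 question, and nothing places it in a BCTOS subscale.

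**The None-to-Large items may be clear on the real form.** A column heading could be missing from the copy reviewed, and patients may naturally read the scale as degree of problem or difference. The documents do not state the BCTOS reference or scoring, so they cannot settle what the heading should be. The count of 10 is a judgement on wording. This stands as a reason to check the source form first. But the stem itself is running text, and the analysis plan gives no scoring direction either.

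**The loss of power is hypothetical.** No document gives a share of reverse readers. If everyone reads the items alike, direction costs nothing. This stands; the table shows a range, not an estimate.

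**Two stronger readings are tempting.** A reader might infer that the affected scores cannot be compared between arms at all. The documents do not support that: both randomised arms complete the same forms, and the models in 16.631 can be run. A reader might also infer that fatigue is measured on a pain scale, because Appendix IV prints the fatigue question a second time above a 0 to 10 row ending in "Worst pain imaginable", with no pain question. That table is visibly broken, so a pain row may simply have been lost or displaced. Appendix II also has a properly anchored fatigue item: "Your level of fatigue, on average? *Response scale 1 to 10, with 1 = no fatigue; 10 = fatigue as bad as it could be". The Appendix IV row is a query and nothing more.

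**Conclusion.** The point holds as a minor one. The burn anchor is wrong as printed. The 24 None-to-Large items lack a stated reference and direction, which leaves 10 of them without a clear scoring direction unless the source form supplies one.

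Until that is settled, those items, and the BCTOS subscales that include them, are hard to interpret, and arm contrasts on them may be weakened. In the illustration, if 20% of patients in each arm read an item in reverse, the difference falls from 0.40 to 0.24 and power from 57% to 19%.

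The conclusion that no false difference arises assumes that misreading is equally common in both arms, which the shared forms make reasonable. The effect is confined to exploratory endpoints.

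**What to change.** 1. In Appendix II, question 10, change the upper anchor of the burn item to burn severity.
2. Check the source form of the None-to-Large items. If it has no heading that settles the matter, state reference and direction in both stems, for example difference or problem on the treated side, with None as the best answer.
3. In 16.631, state the scoring direction of each item and which items form each subscale. Report items collected under the present wording separately, or in a sensitivity analysis with and without them. Dropping them outright would remove up to 10 of 24 items, including 5 of the 6 breast items, on a reading not yet verified.
4. Check the fatigue/pain row of Appendix IV against the source form, and correct it only if the fault is there too.

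The cost is small: a wording correction and a few sentences in 16.631, best settled before the arms are compared. Section 11.4 says that the questionnaires are standard of care for all patients, so the form change may need agreement beyond the trial. The addition to 16.631 does not depend on that.
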